9. OUTSIDE PHYSICIAN PARTICIPATION DURING TREATMENT

- 9.1 MDACC Physician communication with the outside physician is required prior to the patient returning to the local physician. This will be documented in the patient record.
- 9.2 A letter to the local physician outlining the patient's participation in a clinical trial will request local physician agreement to supervise the patient's care
- 9.3 Protocol required evaluations outside MDACC will be documented by telephone, fax or e-mail. Fax and/or e-mail will be dated and signed by the MDACC physician, indicating that they have reviewed it.
- 9.4 Changes in drug dose and/or schedule must be discussed with and approved by the MDACC physician investigator, or their representative prior to initiation, and will be documented in the patient record.
- 9.5 A copy of the informed consent, protocol abstract, treatment schema and evaluation during treatment will be provided to the local physician. A copy of the REMS (Risk Evaluation and Mitigation Strategy) documentation on ponatinib will also be provided to the local physician.
- 9.6 Documentation to be provided by the local physician will include drug administration records, progress notes, reports of protocol required laboratory and diagnostic studies and documentation of any hospitalizations.

9.7 The home physician will be requested to report to the MDACC physician investigator all life threatening events within 24 hours of documented occurrence.

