8. REPORTING REQUIREMENTS

Adverse event reporting will be as per the NCI criteria and the MDACC Leukemia Specific Adverse Event Recording and Reporting Guidelines (Appendix C).

The descriptions and grading scales found in the revised NCI Common Terminology Criteria for Adverse Events (CTCAE) version 4.0 will be utilized for adverse event reporting. (http://ctep.cancer.gov/reporting/ctc.html).

These adverse events will be recorded in the Case Report Form (CRF):

- Any grade adverse event that is possibly, probably, or definitely related to the study drug(s)
- All serious adverse events regardless of attribution to the study drug(s)
- Any grade adverse event regardless of attribution to the study drugs(s) that results in any dose modification

Patients will be registered in CORe. Prometheus will be used for data entry and AE capture.

Baseline events will be recorded in the medical history section of the case report form (Prometheus) and will include the terminology event name, grade, and start date of the event. Abnormal laboratory values or test results will not be recorded or reported as adverse events unless it leads to therapeutic intervention, results in dose modification or interruption, or meets the protocol definition of a DLT or SAE.

AEs will be shared with AbbVie on an annual basis.

Serious Adverse Event Reporting (SAE) for M. D. Anderson-sponsored IND Protocols

An adverse event or suspected adverse reaction is considered "serious" if, in the view of either the investigator or the sponsor, it results in any of the following outcomes:

- Death
- A life-threatening adverse drug experience any adverse experience that places the
 patient, in the view of the initial reporter, at immediate risk of death from the adverse
 experience as it occurred. It does not include an adverse experience that, had it occurred
 in a more severe form, might have caused death.
- Inpatient hospitalization (with the exception of planned hospitalization period for cycle 1) or prolongation of existing hospitalization
- A persistent or significant incapacity or substantial disruption of the ability to conduct normal life functions.
- A congenital anomaly/birth defect.

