Important medical events that may not result in death, be life-threatening, or require hospitalization may be considered a serious adverse drug experience when, based upon appropriate medical judgment, they may jeopardize the patient or subject and may require medical or surgical intervention to prevent one of the outcomes listed in this definition. Examples of such medical events include allergic bronchospasm requiring intensive treatment in an emergency room or at home, blood dyscrasias or convulsions that do not result in inpatient hospitalization, or the development of drug dependency or drug abuse (21 CFR 312.32).

Important medical events as defined above, may also be considered serious adverse
events. Any important medical event can and should be reported as an SAE if deemed
appropriate by the Principal Investigator or the IND Sponsor, IND Office.

All events occurring during the conduct of a protocol and meeting the definition of a SAE must be reported to the IRB in accordance with the timeframes and procedures outlined in "The University of Texas M. D. Anderson Cancer Center Institutional Review Board Policy for Investigators on Reporting Unanticipated Adverse Events for Drugs and Devices". Unless stated otherwise in the protocol, all SAEs, expected or unexpected, must be reported to the IND Office, regardless of attribution (within 5 working days of knowledge of the event).

- All life-threatening or fatal events, that are unexpected, and related to the study drug, must
 have a written report submitted within 24 hours (next working day) of knowledge of the event
 to the Safety Project Manager in the IND Office.
- Unless otherwise noted, the electronic SAE application (eSAE) will be utilized for safety reporting to the IND Office and MDACC IRB.
- Serious adverse events will be captured from the time of the first protocol-specific
 intervention, until 30 days after the last dose of drug, unless the participant withdraws
 consent. Serious adverse events must be followed until clinical recovery is complete and
 laboratory tests have returned to baseline, progression of the event has stabilized, or there
 has been acceptable resolution of the event.
- Additionally, any serious adverse events that occur after the 30 day time period that are
 related to the study treatment must be reported to the IND Office. This may include the
 development of a secondary malignancy.

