Adverse event reporting will be as per the NCI criteria and the MDACC Leukemia Specific Adverse Event Recording and Reporting Guidelines, located in protocol appendix A.

- An adverse event is the appearance or worsening of any undesirable sign, symptom, or
 medical condition occurring after starting the study drug even if the event is not considered to
 be related to study drug. Medical conditions/diseases present before starting study drug are
 only considered adverse events if they worsen after starting study drug. Abnormal laboratory
 values or test results constitute adverse events only if they induce clinical signs or symptoms,
 are considered clinically significant, or require therapy.
- The investigator (or physician designee) is responsible for verifying and providing source documentation for all adverse events and assigning the attribution for all adverse events for subjects enrolled.

Reporting to FDA:

• Serious adverse events will be forwarded to FDA by the IND Sponsor (Safety Project Manager IND Office) according to 21 CFR 312.32.

It is the responsibility of the PI and the research team to ensure serious adverse events are reported according to the Code of Federal Regulations, Good Clinical Practices, the protocol guidelines, the sponsor's guidelines, and Institutional Review Board policy.

Reporting to Abbvie:

Product Complaints: In addition to compliance with all FDA requirements pursuant to 21 CFR 211 and 21 CFR 820, Principal Investigator will report to AbbVie within 24 hours any suspected quality defect in an AbbVie Product or its AbbVie-provided packaging, labeling, or medical device component (collectively, "Product Complaint"). Principal Investigator will report Product Complaints that involve an AbbVie Product, whether AbbVie has supplied the AbbVie Product used in the Study or not. AbbVie's contact for reporting Product Complaints shall be [contact]

In addition to compliance with all FDA reporting requirements pursuant to 21 C.F.R. § 312, the PI shall:

- report to AbbVie all serious adverse events experienced by a study subject receiving an AbbVie
 product within 24 hours of learning of the event regardless of the relationship of the event to the
 AbbVie product. Principal Investigator shall make available to AbbVie promptly such records as
 may be necessary and pertinent to investigate any such event, if specifically requested by
 AbbVie; and in addition, report all non-serious adverse events of tumor lysis syndrome for

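### Section 9.7 asks home physicians for prompt notice of life-threatening events only, so from cycle 2 another local hospitalization could stay unknown to the center for nominally up to 28 days

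*Combined protocol and SAP*

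**What the plan says.** Section 9 governs patients who go back to a local physician during treatment. Its reporting clause, 9.7, reads: "The home physician will be requested to report to the MDACC physician investigator all life threatening events within 24 hours of documented occurrence." Section 9.6 lists the records that the local physician supplies, among them "reports of protocol required laboratory and diagnostic studies and documentation of any hospitalizations", with no time limit. Section 9.4 adds a rule on study treatment: "Changes in drug dose and/or schedule must be discussed with and approved by the MDACC physician investigator, or their representative prior to initiation".

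Section 8 defines seriousness more widely. Besides life-threatening events it lists death, lasting incapacity, congenital anomaly, other important medical events, and "Inpatient hospitalization (with the exception of planned hospitalization period for cycle 1) or prolongation of existing hospitalization". The center must report every SAE to the venetoclax supplier "within 24 hours of learning of the event regardless of the relationship of the event" to the product. It must also report every SAE to the IND Office within 5 working days of knowing of it.

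Section 4.3 allows all therapy from cycle 2 to be given to outpatients. Section 6.2 sets the toxicity assessment, blood count and chemistry once before each cycle from cycle 2. In cycle 1 the blood count is taken once or twice weekly and chemistry at least weekly.

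**The concern.** The clause that brings information in from the home physician is narrower than the SAE definition that the center has to act on. Of the serious outcomes in section 8, only life-threatening events carry a deadline for the home physician. An unplanned admission that does not threaten life is an SAE, yet its only route into the center under section 9 is a record request without a date.

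The center's two deadlines do not repair this, because both run from the moment it knows. It can meet them in full while an admission remains unknown to it.

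What is at stake is patient safety. Section 4.5 requires action on ponatinib for several events that can lead to an admission without an immediate threat to life. Symptomatic grade 3 pancreatitis calls for a hold until grade 1 and then a lower dose. A leg deep venous thrombosis calls for a lower dose or discontinuation. If the center does not know, it cannot apply these rules.

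**Working it through.** No sample size, power or boundary figure in the plan bears on this point. The check sets the reporting steps side by side and works out the longest interval that the schedule allows.

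**Step 1. The chain.** Time from event to outside report = (time until the center learns) + (the center's own deadline).

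| Event in a locally managed patient | Deadline for the home physician | Center to supplier | Center to IND Office |
|---|---|---|---|
| Life-threatening | 24 hours from documented occurrence (9.7) | 24 hours from learning | 5 working days from knowledge |
| Unplanned admission, not life-threatening | none; records only (9.6) | 24 hours from learning | 5 working days from knowledge |

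In the second row the first term is limited only by the next scheduled contact.

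**Step 2. The scheduled interval.**

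- Cycle 1: chemistry is at least weekly, so about 7 days at most. Earlier discovery is likely.
- Cycles 2-4: one toxicity assessment per 28-day cycle, so 28 days. Intrathecal doses on days 2 and 7 (each ± 3 days) are an extra occasion on which an event may come to light. Counted from the second of these, the interval is 28 − 7 = 21 days, with a range from 28 − 10 = 18 to 28 − 4 = 24. They are not scheduled toxicity assessments.
- Maintenance: no intrathecal doses are listed, so 28 days in each of up to 24 cycles.
- Delayed next cycle: section 4.5 allows venetoclax to be interrupted for up to 14 days after a cycle that ends in CRi or a leukemia-free marrow. If the pre-cycle assessment moved with it, the interval would be 28 + 14 = 42 days. This is a loose upper limit, because such a hold implies that marrow and counts were looked at when the cycle ended.

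If admissions fell evenly over a 28-day cycle (an assumption), the mean wait to the next assessment would be 28/2 = 14 days.

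**Step 3. The whole chain, from cycle 2.** For a life-threatening event, the supplier hears within 1 + 1 = 2 days. For another admission that nobody reports between assessments, it hears within nominally 28 + 1 = 29 days. The IND Office hears within nominally 28 days plus 5 working days.

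**Step 4. Would routine tests reveal it?** Not necessarily. After screening, section 6.2 has amylase and lipase checked only when clinically indicated, so an admission for pancreatitis need not show in the center's scheduled results. From cycle 2 the other scheduled blood tests also come once per cycle.

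**Step 5. Effect on the statistical design.** The thresholds and priors in section 10 give the boundaries in Tables 2 and 3, and a recalculation with beta posteriors reproduced each of them. They do not depend on how fast a report arrives. At the stated accrual of about 10 patients a year, 10 × 28/365.25 = 0.77 patients would be expected to enroll during a 28-day delay.

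**The case against.** The strongest defense is 9.4. A local physician who wants to stop or lower ponatinib must first obtain the center's approval, so an admission for pancreatitis in which the drug is interrupted already produces a call. Section 9.1 also requires documented contact with the outside physician before the patient goes back to local care, which is a natural time to give reporting instructions. Section 8 makes the principal investigator and the research team responsible for SAE reporting, and section 7.2 says that toxicity is monitored continuously. The section 8 deadlines run from knowledge, so 9.7 contradicts none of them.

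Much of this stands, and it narrows the point. What remains is an admission in which the local physician continues the study drugs unchanged and sees no reason to call. There 9.4 is not triggered, 9.1 is already past, and the center's duty has not begun. Continuous monitoring is stated without a route from the local physician. The appendix with the leukemia reporting guidelines and the letter described in 9.2 were not available for this review, and either may set a timeline. Even so, the clause in the protocol itself would still be narrower than its own SAE definition.

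A reader might go further and infer that local physicians are not told of the section 4.5 venetoclax reductions for CYP3A inhibitors, because 9.5 says "A copy of the informed consent, protocol abstract, treatment schema and evaluation during treatment will be provided to the local physician", adds the ponatinib REMS, and names neither section 4.5 nor section 5. The documents do not support that inference. The consent, the abstract and the 9.2 letter could not be read here and may carry exactly those instructions.

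**Conclusion.** The point holds as a minor patient-safety improvement, with medium confidence. From cycle 2, a local admission that is not life-threatening and prompts no proposed study-drug change has no deadline for reaching the center. It could wait until the next toxicity assessment, nominally up to 28 days.

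That figure is a scheduled interval, not an observed delay. A call under 9.4, an intrathecal or rituximab visit, a patient's own call or an earlier test can shorten it, and a late next cycle can lengthen it. The documents give neither the share of patients managed locally nor the rate of such admissions, so the number of patients affected cannot be estimated.

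Two larger conclusions would be wrong. A reader might infer that phase I dose-limiting toxicities would be missed. The non-hematologic window lies within cycle 1, where blood tests are at least weekly, and escalation needs a toxicity summary and IND Office approval, so no delay is shown there. A reader might also infer that the phase II stopping rules are compromised. No boundary, sample size or escalation rule changes.

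**What to change.** Reword 9.7 so that the home physician is requested to report, within 24 hours of becoming aware, every serious adverse event as defined in section 8, with deaths and unplanned hospitalizations named explicitly. Section 9.6 can stay as it is, since the records may follow the notice.

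The cost is one changed sentence and a few more reports from local physicians, mainly of admissions whose records 9.6 already asks for. There is no need to request routine 24-hour notice of non-serious cytopenias, or to add a separate request for suspected dose-limiting toxicities.

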10. STATISTICAL METHODOLOGY

This is a single arm, open label, phase I/II study to assess the MTD and the efficacy of the combination regimen of venetoclax, ponatinib and corticosteroids in patients with relapsed/refractory Ph+ ALL.

Phase I: The primary objective is to determine the optimal dosing and schedule of the combination regimen. This aim will consist of a phase I trial to determine the maximum tolerated dose (MTD) of venetoclax when given in combination with ponatinib and dexamethasone. A standard 3+3 dose escalation design will be employed: Two dose levels of venetoclax will be explored. Patients will be treated in cohorts of size three to six and the dosage will be escalated if the clinical toxicity is acceptable. A dose-limiting toxicity (DLT) is defined in "Definition of DLT" in section 4.8.

The design is constructed to reduce the chance of escalating the dose when the probability of DLT is high, and increase the chance of escalating the dose when the probability of DLT is low. The MTD is defined as the highest dose level where a DLT occurs within at most one out of six patients treated. The escalation scheme is as follows:

- (1) If none of the initial three patients in a cohort experiences a DLT, then a new cohort of three patients will be treated at the next higher dose level.
- (2) If one of the three patients in a cohort experiences a DLT, then up to three additional patients will be treated at the same dose. Escalation will continue if only one of the six patients experiences DLT.
- (3) If two or more patients in a cohort experience DLT, then the MTD will have been exceeded, and no further dose escalation will occur. The previous dose level will be considered the MTD.
- (4) If only three patients were treated at a dose level under consideration as the MTD, then up to three additional patients will be accrued. If no more than one of the six patients at that dose level experience a DLT, then that dose level will be confirmed as the MTD. If two or more patients in that cohort experience DLT, then the previous dose level will be studied in the same fashion.

The MTD is defined as the highest dose studied for which the observed incidence of DLT is less than 33%. Frequencies of toxicities will be tabulated according to the NCI Common Toxicity Criteria. Patients will be continued to be followed for one year for evidence of late toxicity.

Table 1 below gives the probabilities of dose escalation based on true DLT risk in the 3+3 design.

					T	rue DLT ra	ate		
	10%	20%	30%	40%	50%	60%	70%	80%	90%
Probability of									
escalation	0.91	0.71	0.49	0.31	0.17	0.08	0.03	0.01	0.001

A minimum of 6 patients and a maximum of 12 patients will be enrolled to the phase I portion of the trial.

Phase II: The primary objective is to determine the overall response rate, defined as the rate or CR + CRi occurring at the end of 2 cycles of treatment. A total of up to 26 patients will be in the phase II part including patients who received the MTD dose level in the phase I portion and those enrolled in the phase II portion of the study. The target overall response (OR) rate is 60%. This regimen of the combination treatment will be considered worthy of further investigation if it elicits an increase in OR to 60% with

acceptable toxicity. A >15% drug-related grade 4-5 toxicity rate is considered unacceptable. Thus, interim monitoring rules, assuming the prior distributions below, were constructed that meet the following two conditions,

- 1) Stop if $Prob[p(OR, E) < 0.60 \mid data] > 0.975$, or
- 2) Stop if $Prob[p(TOX, E) > 0.15 \mid data] > 0.8$,

where p(OR, E) and p(TOX, E) are the true OR and toxicity rates for the combination treatment. The first rule provides for stopping the study if the data suggest that it is unlikely (i.e., probability < 2.5%) that OR rate of the combination treatment is greater than 0.6. The second condition will stop the study early if excessive therapy-related grade 4-5 toxicity (>15%) is highly probable (i.e., probability >80%) for the combination treatment. Monitoring for toxicity and futility will not begin until 6 patients have been evaluated, and cohort size for future evaluations is 2.

The monitoring rule for the toxicity rate, based on these assumptions and monitoring conditions above is found in Table 2. For example, accrual will cease if 2 or more patients experience toxicities among the first 6 patients. Toxicities will be continually monitored and will count towards this stopping rule if they occur while the patient is still on study.

Table 2. Stop accrual if there are this many drug-related grade 4-5 toxicities among the number of patients evaluated					
# patients evaluated	# patients with toxicities				
6	2-6				
8-10	3-10				
12-16	4-16				
18-20	5-20				
22-24	6-24				
26	Stop due to maximum sample size				

Monitoring the OR rate, based on the above assumptions and monitoring conditions is found in Table 3. For example, accrual will cease if no patients experience an overall response in the first 6 patients treated.

Table 3. Stop accrual if there are th number of patients evaluated	is many response (i.e., # patients with overall response) among the	
# patients evaluated	# patients with overall response	
6	0	
8	0-1	
10	0-2	
12	0-3	
14	0-4	
16	0-5	
18	0-6	
20	0-7	
22	0-8	
24	0-9	
26	Stop due to maximum sample size	

Multc Lean Desktop (version 2.1.0) was used to generate the toxicity and futility stopping boundaries and the operating characteristics table (Table 3). In order to utilize the software for the design, a 60% constant rate and beta (1.2, 0.8) priors were assumed for the standard treatment response rate and experimental treatment response prior distribution, respectively. In addition, a 15% constant rate and beta (0.3, 1.7) priors were assumed for the standard treatment toxicity rate and experimental treatment toxicity prior distribution, respectively.

The probability of stopping the study early if the true OR of the combination treatment was 60% and the true toxicity rate was 15% was 39.24%. Probabilities of stopping early for high true toxicity rates (i.e., 40%) were 98.27% when the true OR was 60% and 99.79% when true OR rate was 30%.

True Toxicity Rate	True OR	Prob(stop the trial early)
0.10	0.30	0.9028
	0.40	0.6445
	0.50	0.3561
	0.60	0.2064
	0.70	0.1688
0.15	0.30	0.9256
	0.40	0.7278
	0.50	0.5070
	0.60	0.3924
	0.70	0.3636
0.2	0.30	0.9506
	0.40	0.8193
	0.50	0.6727
	0.60	0.5966
	0.70	0.5775
0.3	0.30	0.9861
	0.40	0.9490
	0.50	0.9076
	0.60	0.8861
	0.70	0.8808
0.4	0.30	0.9979
	0.40	0.9922
	0.50	0.9860
	0.60	0.9827
	0.70	0.9819

Secondary objectives include: the rate of minimal residual disease negativity by PCR for BCR-ABL1 transcripts, proportion of patients proceeding to ASCT, relapse-free survival, overall survival, and the safety of the combination regimen.

The investigator is responsible for completing toxicity/efficacy summary reports and submitting them to the IND office Medical Affairs and Safety Group for review. These should be submitted as follows:

- Phase I: A toxicity summary must be submitted after the first 3 evaluable patients, complete 1
 cycle of study treatment, and every 3 evaluable patients thereafter, IND office approval must be
 obtained prior to advancing/changing dose levels.
- Phase II: A efficacy/toxicity summary must be submitted after the first 6 evaluable patients complete the second cycle of study treatment, and every 2 patients thereafter.

A copy of the cohort summary should be placed in the Investigator's Regulatory Binder under "sponsor correspondence".

Analysis Plan: Demographic/clinical characteristics and safety data of the patients will be summarized using descriptive statistics such as mean, standard deviation, median and range.

For the primary efficacy analysis, we will estimate the OR for the combination treatment (defined as the proportion of patients achieving CR or CRi after 2 cycles of treatment), along with the 95% credible interval. This regimen will be considered worthy of further investigation if an OR rate of at least 60% is achieved. Patients who drop out of the study before completing 2 cycles will be treated as "failures" for the primary analysis. The association between response and patient's clinical characteristics such as apoptotic protein expression, will be examined by Wilcoxon's rank sum test or Fisher's exact test, as appropriate.

The proportion of patient achieving CMR (as assessed by PCR for BCR-ABL transcripts) after 2 cycles of therapy will be estimated. The proportion of patients proceeding to ASCT and median time to ASCT will also be reported.

Kaplan-Meier curves will be used to estimate unadjusted OS and RFS distributions. Overall survival defined as the time from treatment initiation to death or last follow-up. RFS is defined as the time from the date of remission to relapse from CR or death from any cause whichever occurs first. Median OS and RFS as well as 1-year OS and RFS rates will be reported. Comparisons of time-to-event endpoints by important subgroups will be made using the log-rank tests.

Patients who enrolled in the phase I part of the trial who receive the MTD of venetoclax will be included in all efficacy analyses.

Toxicity type, severity and attribution will be summarized for each patient using frequency tables.

Sample Size: We will treat up to 26 patients at the recommended phase II dose (including patients who received the MTD dose level in the phase I portion and those enrolled in the phase II portion of the study). For the efficacy endpoint, with a sample size of 26 patients, If the study is not stopped early and 26 patients have been treated and evaluated in the study, assuming 16 of the 26 patients achieve OR, then the 95% credible interval for OR rate will be (0.43,0.79).

Approximately 10 patients per year are expected to be enrolled. The total study duration is expected to be 5 years (3 years of new patient enrollment, plus an additional 2 years of follow-up).

